## Promoting Follow-Up Care Self-Management for Adolescent and Young Adult (AYA) Childhood Cancer Survivors

[name], MPH

ion			the follow-up		
-----	--	--	---------------	--	--

Sample size was based on the primary feasibility aim, but we also calculated detectable group difference in the primary outcome of the RTQ Adolescent Responsibility total score at the 6-week post-intervention time. Based on survey data, we expect AYA survivors to score an average of 2.57 ( $SD = 0.83$ ) at baseline. Using an independent t-test assuming the control group remains at baseline levels and two-sided alpha of .05, we have 80% power to detect a group difference of 0.66 in the outcome. This would represent the intervention group increasing from “sometimes” to “often” being responsible, which we consider clinically meaningful.

Up to 20 mentors will participate. Mentors will be matched 1:1 with AYA survivors; each mentor may agree to work with up to 5 individuals. As in Phase 2, we expect that several mentors will choose to mentor more than one individual, so a sample size of up to 20 is reasonable.

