#### ***3.1. Duration of Study***

Phase 1: Participants will be asked to complete a one-time interview lasting approximately 60 minutes.

Phase 2: Participants will be asked to complete the intervention over a period of 6 weeks. Participants will be asked to complete 6-week online self-management educational modules and 6 weekly peer mentor calls to facilitate engagement with the online modules and offer specialized support.

Phase 3A: Usability sessions will last approximately 1-hour. Given that usability testing is iterative and design changes are made in response to participant feedback, we will ask some participants if they are willing to review the product another time after changes are made, up to a total of five times. Each session is voluntary and conducted in a way to minimize participant burden.

Phase 3B: Participants assigned to the intervention will be asked to complete it over a period of approximately 8 weeks (which includes 6 peer mentor calls and five corresponding online modules). All participants will be asked to complete surveys at four time points: baseline, immediate post-intervention (~8 weeks after baseline), 3-month follow-up (~5 months after baseline), and 9-month follow-up (~12 months after baseline).

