### **3.3 Sample Size Justification**

Phase 1: Total sample size is 24-28, including 10 AYA survivors, 10 parents of AYA survivors, and 4-8 physicians who work with AYA survivors. Qualitative data will be analyzed on a continuing basis. Pooling data across participants, we expect 24-28 interviews will be adequate to achieve data saturation (that is, no new themes emerge from additional participants).

Phase 2: 40 AYA survivors and 20 peer mentors will be recruited for the pilot trial to evaluate feasibility (primary objective) and preliminary outcomes (secondary objective). As this is a feasibility study, we recognize we are underpowered to detect small or medium effects. Published data suggest 5-9% of survivors are African American or Hispanic; data from the NJSCR show greater diversity, with 11.6% of patients diagnosed with cancer at age 10-19 during the period of 2008-2012 reporting as African American, 19% reporting as Hispanic, and 5.7% as Asian American/Pacific Islander. We will oversample these groups.

Phase 3A: Up to 20 AYA survivors will be recruited for usability testing of the online intervention. Given the preliminary work conducted in Phase 2, we expect 12-20 sessions will achieve data saturation (i.e., no new issues emerge according to pre-specified stopping criteria). Usability testing is designed to be iterative in that changes can be made to the site after a small number of participants. Therefore, participants who agree may be asked to complete multiple usability sessions over the course of a few months to provide additional feedback on changes or new features added. Thus we expect about 12 to 20 participants will be needed to achieve data saturation.

Phase 3B: Total sample size is 50 AYA survivors. We chose the sample size and decision rules so that the probability of declaring feasibility would be approximately 5% under unacceptable rates of acceptance/completion and exceed 95% under acceptable rates. If true acceptance and completion rates were 41% and 70%, respectively, which we consider too low to move to an efficacy trial, then the probability of declaring feasibility would be 5%.

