### Phase 3B:

**Data Management:** The same procedures used in Phase 2 will be used in Phase 3B, with the exception that TigerConnect (previously called TigerText) will be used for secure messaging as well as secure videoconferencing (instead of doxy.me). Additionally, TigerConnect now allows for secure file transfer so that peer mentors can securely transfer audio recordings to the study team either via Rutgers LiFT or TigerConnect. For participants who consent to be contacted for future studies, the study team will store their contact information separately from research records on the PI's secure One Drive, with access granted only to the PI, study coordinator, and limited authorized research staff. We will store this information for up to 10 years from date of consent.

We will utilize HIPAA compliant Qualtrics survey tool to request the name and contact information of the physician they have seen in the past 12 months to understand their health care utilization during the study period and to obtain their electronic signature on the Release of Medical Record form. Any paper copies will be kept in a locked filing cabinet in the PI's office.

**Data Analysis:** We will examine feasibility through study enrollment rates, retention rates, usability/engagement with online modules and peer mentor, barriers to engagement, and reasons for study drop out. Descriptive analyses (frequencies, means, confidence intervals) will be used to evaluate hypotheses regarding enrollment ( $>50\%$ ), retention ( $>80\%$  complete all surveys), and intervention completion ( $>75\%$  modules/mentor calls). Multilevel modeling (MLM) will be used to examine differences between the intervention and usual care groups over time on transition readiness (RTQ Adolescent Responsibility and TRI total scores). Our primary analysis will consider both time and treatment to be categorical with an interaction between the two. The interaction will be assessed to determine whether change in transition readiness differs between the two groups. The MLM approach assumes any missing observations are missing at random but includes all observed data. Exploratory analyses of additional outcomes (e.g., self-efficacy, adherence to medical appointments and screenings, and health behaviors) will use the identity link or the logit link as appropriate for continuous or binary outcomes.

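### The Phase 3B power statement is for a one-visit t-test at a 6-week time point that does not exist, while the primary analysis is a time-by-treatment interaction with no named visit or contrast

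*Combined protocol and SAP*

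**What the plan says.** Section 3.3 (Sample Size Justification, Phase 3B) sets the total at 50 survivors on feasibility grounds: "Sample size was based on the primary feasibility aim, but we also calculated detectable group difference". That second calculation concerns the "primary outcome of the RTQ Adolescent Responsibility total score at the 6-week post-intervention time". It takes a baseline mean of 2.57 with SD 0.83 and describes the test thus: "Using an independent t-test assuming the control group remains at baseline levels and two-sided alpha of .05". The result is "we have 80% power to detect a group difference of 0.66 in the outcome".

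Section 3.1 lists four Phase 3B surveys: baseline, "immediate post-intervention (~8 weeks after baseline"), about 5 months and about 12 months. The measures table in section 4.2 uses the same schedule. It collects RTQ at all four time points and TRI at the first three only. Six weeks is the post-intervention time of Phase 2 (sections 3.1 and 4.2).

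Section 5 (Phase 3B, Data Analysis) fits a multilevel model to the RTQ Adolescent Responsibility and TRI total scores: "Our primary analysis will consider both time and treatment to be categorical with an interaction between the two". It then says the interaction will be used to judge whether change differs between arms. It names no primary visit, contrast or degrees of freedom.

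**The concern.** Two things do not line up.

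**The time point.** No Phase 3B survey falls at 6 weeks, whether that means 6 weeks after baseline or 6 weeks after the programme ends (about week 14). The only place where the plan ties the primary efficacy outcome to a visit therefore points to a visit that is not in the schedule.

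**The quantity.** The power statement is for the difference between two group means at one visit. The primary analysis assesses an interaction over all visits. A joint interaction test can be significant because of a difference in change at any visit and in either direction, so it gives neither the direction nor the timing of an effect. Hypothesis 4 is directional: it expects greater improvement with the intervention. If no contrast is named beforehand, the team would choose which visit to emphasise after seeing the data. A reader would also take the 80% as the power of the primary test, which it is not.

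**Working it through.** **Inputs from the plan:** N = 50, SD 0.83, difference 0.66, two-sided alpha 0.05 (section 3.3); four RTQ time points (sections 3.1 and 4.2).

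**Assumptions, because the plan gives no figure:** 1:1 allocation (25 per arm); SD 0.83 at every visit; compound symmetry with correlation ρ = 0.3, 0.5 or 0.7; no baseline difference; the pattern of effect over time.

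**1. The plan's own figure.** The standard error of a difference in means is 0.83 × √(2/25) = 0.2348.
- Detectable difference, normal approximation: (1.960 + 0.842) × 0.2348 = 0.658. With the exact t distribution (48 df) it is 0.671.
- Power at 0.66: 80.3% (normal) or 78.7% (exact t).

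The stated 0.66 reproduces. Visit time does not enter the formula, so changing 6 to 8 weeks leaves it unchanged. The calculation uses all 50 participants. With 20 per arm (40 completers, the Table 1 retention rule), power at 0.66 is 71% (normal) or 69% (exact t).

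**2. The joint interaction test for RTQ.** Let m be the between-arm differences in change from baseline at the three later visits. Under compound symmetry the noncentrality is

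λ = n / [2 × SD² × (1 − ρ)] × [Σm² − (Σm)²/4].

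The test is F with 3 numerator df; 48 denominator df are used here. At ρ = 0.3 and n = 25 the multiplier is 25 / (2 × 0.6889 × 0.7) = 25.92.
- Sustained (0.66 at each visit): bracket = 1.3068 − 0.9801 = 0.3267, so λ = 8.47.
- Fading (0.66, 0.44, 0.22): bracket = 0.6776 − 0.4356 = 0.2420, so λ = 6.27.
- One visit only (0.66 at any one of the three): bracket = 0.4356 − 0.1089 = 0.3267, the same as sustained.

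**3. The week-8 contrast from the same data.**
- Change from baseline: SE = 0.83 × √[2(1 − ρ)] × √(2/n).
- Baseline-adjusted: SE = 0.83 × √(1 − ρ²) × √(2/n). At ρ = 0.5 and n = 25 this is 0.2033, so 0.66/0.2033 = 3.25.

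| Power, complete data | ρ = 0.3 | ρ = 0.5 | ρ = 0.7 |
|---|---|---|---|
| 3-df interaction, sustained, 25 per arm | 64% | 80% | 96% |
| 3-df interaction, fading, 25 per arm | 50% | 66% | 88% |
| Week-8 change contrast, 25 per arm | 64% | 79% | 95% |
| Week-8 baseline-adjusted, 25 per arm | 82% | 89% | 97% |
| 3-df interaction, fading, 20 per arm | 40% | 54% | 79% |
| Week-8 baseline-adjusted, 20 per arm | 73% | 81% | 93% |

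The 20-per-arm rows are a complete-case lower bound; the multilevel model would also use partial data. With 144 denominator df instead of 48, the 25-per-arm interaction rows become 67%, 82% and 97% (sustained) and 53%, 69% and 90% (fading).

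**4. What the joint test distinguishes.** By step 2, an effect of 0.66 at week 8 alone and an effect of 0.66 at month 12 alone have the same λ and hence the same power. Significance by itself does not separate them.

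**The case against.** The best defence is that this is a feasibility pilot with preliminary efficacy aims, that the 6-week label is a carry-over from Phase 2 with no numerical effect, and that the model contains everything needed. Much of this stands, and it rules out several stronger conclusions that a reader might draw.

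- **That the planned model cannot estimate the powered difference.** It can. With time and treatment categorical, the between-arm difference at about 8 weeks, and the difference in change to that visit, both come from the same fit. What is missing is a statement that this is the primary quantity.
- **That the interaction test is always weaker.** It is not. With a sustained 0.66 it matches the week-8 change contrast. If the effect were 0.66, 0.66 and 0.80, it would have 73%, 87% and 98% power, against 64%, 79% and 95%. The loss appears under the fading pattern, which is an assumption. The higher figures for the baseline-adjusted contrast come largely from baseline adjustment, a separate gain in precision.
- **That the plan prescribes a 3-df test.** Section 5 states neither a joint test nor its df. That is the natural reading, and it gives 3 df for RTQ but 2 df for TRI.
- **That Hypothesis 4 asks specifically about the visit just after the programme.** It names no visit. An interaction on change does address it, but without giving direction or timing.
- **That N = 50 is undermined.** It rests on the feasibility rules, which do not depend on this test.

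The pilot label does not remove the point itself. The protocol declares a primary outcome, a primary analysis, an alpha level and a power, and these should refer to the same quantity.

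**Conclusion.** The point holds as a mismatch between the power statement and the analysis. The 6-week time point matches no Phase 3B survey, and the stated 80% power belongs to a one-visit t-test rather than to the interaction that section 5 makes primary. For the t-test, 0.66 is about right. For the 3-df RTQ interaction with 25 per arm and complete data, power ranges from about 50% to 96% over the two effect patterns and three correlations tabulated. Those figures rest on assumed 1:1 allocation, constant SD, compound symmetry, correlation and effect pattern, none of which the plan states. Whether power is lost depends on these assumptions. The lack of a named primary visit and contrast does not. The correction is worth making because it settles the primary efficacy estimate before the data are seen, at almost no cost. It is not a reason to change the sample size.

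**What to change.** 1. In section 3.3, change the 6-week label to the survey at about 8 weeks.
2. In section 5, name the primary efficacy estimate: the between-arm difference in RTQ Adolescent Responsibility at about 8 weeks, from the same multilevel model, with baseline RTQ adjusted or baseline means constrained equal. An unadjusted change contrast would also be valid but less precise.
3. Keep the overall interaction, the later visits and TRI as secondary.
4. State power for the named contrast, with the allocation ratio, assumed correlation and attrition.
5. If the interaction is to remain primary, say that it is a joint test, give its df for RTQ and TRI, and restate power with the assumed correlation and effect pattern.

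The cost is protocol wording; no data, visits or participants are added. The downside is that an effect emerging only at 5 or 12 months would be seen only in secondary analyses. If the team regards durability as the main question, it should name that visit instead and report power for it.

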### ***3.4 Subject Selection and Enrollment Considerations***

#### ***3.5.1 Inclusion Criteria***

Phase 1:

Patient eligibility includes:

- (1) age 18-25
- (2) at least 1.5 years from treatment (which is a typical time for preparation to transfer to long-term follow-up care)

Parent eligibility includes:

- (1) caregiver of a pediatric cancer survivor age 18-25 who was primary caregiver at diagnosis
- (2) patient is at least 1.5 years from treatment

Provider eligibility:

- (1) health professional who works with childhood cancer survivors ages 18 to 25

Phase 2:

Peer mentor eligibility includes:

- (1) age 21-29
- (2) at least 1.5 years from treatment
- (3) self-reported primary responsibility for care and “complete readiness” using the Readiness for Transition Questionnaire

Patient eligibility includes:

- (1) age 18-25
- (2) at least 1.5 years from treatment
- (3) currently does not independently self-manage follow-up care according to self-report (i.e., reports low readiness to assume total responsibility for care [score of 1 or 2

**Promoting Follow-Up Care Self-Management for Adolescent and Young Adult (AYA) Childhood Cancer Survivors**

[name], MPH

out of 4 on overall readiness item OR scores <3 on any of the 10-item responsibility scale) using the Readiness for Transition Questionnaire)

**Phase 3A:**

AYA survivor eligibility includes:

- (1) age 18-29
- (2) at least 2 years from treatment for any pediatric cancer diagnosed at age 0-19

**Phase 3B:**

Peer mentor eligibility includes:

- (1) age 21-29
- (2) at least 2 years from treatment
- (3) self-reported primary responsibility for care and “complete readiness” to assume responsibility for care or high scores (3 or 4) on all items from the Readiness for Transition Questionnaire

Patient eligibility includes:

- (1) age 18-25
- (2) at least 2 years from treatment for any pediatric cancer diagnosed at age 0-19
- (3) currently does not independently self-manage follow-up care according to self-report (i.e., reports parent is primarily responsible or low readiness to assume total responsibility for care [score of 1 or 2 out of 4 on overall readiness item OR scores <3 on two or more items of the 10-item responsibility scale) using the Readiness for Transition Questionnaire)

**3.5.2 Exclusion Criteria**

**Phase 1:**

Patient exclusion criteria includes:

- (1) physician- or self-reported cognitive delay or impairment that would prevent self-management of healthcare

Parent exclusion criteria includes:

- (1) patient has physician- or caregiver-reported cognitive delay or impairment that would prevent self-management of healthcare

No provider exclusion criteria

**Phase 2:**

Patient exclusion criteria includes:

- (1) physician- or self-reported cognitive delay or impairment that would prevent self-management of healthcare
- (2) patients with cancer diagnoses that are not typically considered pediatric cancer, including basal and squamous cell skin cancer, breast, colorectal, lung, melanoma, merkel cell skin cancer, ovarian, testicular, kidney cancer diagnosed at age >17, and nasopharyngeal diagnosed at age > 17.

**Phase 3A/3B:**

Patient exclusion criteria includes:

- (1) physician- or self-reported cognitive delay or impairment that would prevent self-management of healthcare
- (2) patients with cancer diagnoses that are not typically considered pediatric cancer, including basal and squamous cell skin cancer, breast, colorectal, lung, melanoma, merkel cell skin cancer, ovarian, testicular, kidney cancer diagnosed at age >17, and nasopharyngeal diagnosed at age > 17.
- (3) Non-English speaker

### ***3.5.3 Subject Recruitment***

Phase 1: We will recruit 10 AYA survivors of childhood cancers and 10 caregivers through the Rutgers Cancer Institute Long-Term Information Treatment-Effects Evaluation (LITE) program. Invitational letters from [name], the Director of the LITE program, will be sent to patients on the CINJ LITE mailing list. Flyers will be posted and handed out in clinic. Potentially eligible participants will be approached at routine LITE clinic visits to describe the study, answer any questions, and assess interest in participating. If a parent does not accompany an AYA survivor to the LITE visit, we will ask interested AYA survivors to share a flyer with their parent(s). AYAs and parents do not have to be dyads to enroll in the study. We will also recruit 4-8 healthcare providers (e.g., physicians, nurse practitioners, social workers, psychologists) who regularly work with AYA pediatric cancer survivors. These providers will be recruited through the Rutgers Cancer Institute of New Jersey as well as through the AYA and Survivorship Working Groups of the Children's Oncology Group because they will have greater expertise and experience with AYA survivors than community providers.

Phase 2: Peer mentors will be recruited via advertisements in the CINJ LITE clinic and newsletter, AYA cancer support groups, and online forums/social media, such as stupidcancer.org. Following the Children's Oncology Group's approach to recruiting patient advocates, potential mentors will complete an application including two letters of recommendation. The PI or study staff will interview candidates to evaluate interpersonal skills, level of commitment to the program, and counseling or related experience. Participants for the randomized trial will be recruited using the New Jersey State Cancer Registry (NJSCR). All participant information and surveillance data from the NJSCR is collected and maintained by the NJSCR following Standard Operating Procedures (see IRB#Pro20140000992 NJSCR SEER Data Repository). Patient contact procedures, tracking, and data release also follows NJSCR Standard Operating Procedures. Per Standard Operating Procedures, NJSCR staff will contact the physician of record for eligible cases to notify the physician about the study and that staff will be contacting the patient. An introductory letter and flyer will be mailed to potential participants. NJSCR staff will make follow-up phone calls to provide additional information and, for patients who express interest in participating, to obtain permission to send their contact information to [name] study staff, who will then contact the patient for further details and discussion of consent.

Phase 3A: AYA survivors will be recruited during routine CINJ LITE clinic visits, via advertisements in the CINJ LITE clinic and newsletter, mailing a recruitment flyer to

CINJ LITE clinic patients, and via online forums/social media, such as Twitter and Facebook (wording of advertisements are submitted for approval as recruitment materials prior to use). At LITE visits, the PI or trained study staff will approach potentially eligible patients to provide a brief description of the study, answer any questions, and, if interested, obtain consent and schedule a feasibility session. For potential participants mailed a recruitment flyer, trained study staff will make follow-up phone calls to provide study information, answer any questions, and, if interested, obtain consent and schedule a feasibility session.

Phase 3B: As done in Phase 2, peer mentors will be recruited via advertisements in the CINJ LITE clinic and newsletter, AYA cancer support groups, and online forums/social media, such as stupidcancer.org. Following the Children's Oncology Group's approach to recruiting patient advocates, potential mentors will complete an application including two references or a letter of recommendation. The PI or study staff will interview candidates to evaluate interpersonal skills, level of commitment to the program, and counseling or related experience. Participants for the randomized trial will be recruited using the New Jersey State Cancer Registry (NJSCR). All participant information and surveillance data from the NJSCR is collected and maintained by the NJSCR following Standard Operating Procedures (see IRB#Pro20140000992 NJSCR SEER Data Repository). Patient contact procedures, tracking, and data release also follows NJSCR Standard Operating Procedures. Per Standard Operating Procedures, NJSCR staff will contact the physician of record for eligible cases to notify the physician about the study and that staff will be contacting the patient. An introductory letter and flyer will be mailed to potential participants. NJSCR staff will make follow-up phone calls to provide additional information and, for patients who express interest in participating, to obtain permission to send their contact information to [name] study staff, who will then contact the patient for further details and discussion of consent. NJSCR staff will send second mailings to participants who they are unable to reach via phone, with an informational sheet and an option for participants to respond via mail. At the end of the study NJSCR will provide investigators with aggregate de-identified data (i.e., age, gender, time since diagnosis, etc.) on refusals, so that a comparison can be made between "refusals" and the "acceptors."

To maximize the enrollment, we will also recruit mentors and participants during routine CINJ LITE clinic visits or by mail. We will include an approved study recruitment flyer and study staff will follow-up with a phone call to answer any questions and, if interested, initiate the consent process.

